11.1.2. Questionnaire with participants

All participants will also be invited to complete a participant questionnaire comprising two sections: 1) personal experiences with HIV treatment and LA CAB+RPV; 2) quality of life as determined through HIV Patient Reported Outcome Measures (HIV PROM) questions. The questionnaire will be administered at three time points as laid out in the Schedule of Activities (see section 12.3.4). The questionnaires will be administered on-line through REDCap unless a paper-based questionnaire is preferred by the participant.

The participants on oral ART will complete a shorter questionnaire on quality of life as determined through HIV Patient Reported Outcome Measures (HIV PROM) at three time points as laid out in the Schedule of Activities (see section 12.3.4)

11.1.3. In-depth interviews with subset of participants

A subset of participants (2-3 per site) will be invited to an in-depth interview where a topic guide of open-ended questions will facilitate a deeper understanding of the participant's experiences and perceptions. Qualitative data from in-depth interviews will be audio-recorded and transcribed for thematic analysis. Participants who are interviewed will be

reimbursed for their time with a £20 shopping voucher. This is in addition to the reimbursement given for completing questionnaires.

11.1.4. Interview and questionnaire with healthcare workers delivering CAB/RPV

A healthcare worker questionnaire will be administered with healthcare workers involved in delivering the long-acting regimen. A focus group discussion / interview will also be conducted with a representative sample of healthcare workers (e.g. Pharmacist, Nurse, Consultant) delivering the long-acting regimen at the participating clinics. This will collect information on implementation approach deployed, experiences and outcomes to date, perceived barriers and facilitators of regimen use on BHIVA-recommended clinical use and compassionate grounds.

11.1.5. Notes review to understand adoption cascade

A registry dataset of patients eligible for LA CAB/RPV will be generated from the main clinic database. Over the following 12 months, the clinic will then quantify the number of patients ever offered a switch to LA CAB+RPV, the number who accept the switch and the number who remain on the regimen for at least 1 year duration. Reasons for not being offered or declining a switch to LA CAB+RPV will be recorded.

[figure not shown]

Figure 2. Schematic of study including qualitative and quantitative aspects

11.2. Study population

The study will be conducted in approximately 10-12 NHS HIV departments in the UK (4-5 in England, 1-2 in Wales, 1-2 in Scotland and 1 in Northern Ireland). To ensure the data are representative of the UK, participating clinics will be distributed across England, Wales, Scotland and Northern Ireland and of varying cohort size (small, medium and large), geographical area (urban; rural) with a diverse clinic population. It is anticipated that 5-20 patients in LA CAB+RPV and 3-6 patients on oral ART will be enrolled from each centre depending on cohort size. Patients who were initiated on LA CAB+RPV within the prior 6

months will be identified by a member of the clinical team or research team, from review of clinic records and databases as appropriate at each centre. Patients beginning LA CAB+RPV in the 6-12 months after site initiation will be eligible to join prospectively.

It is intended that approximately 10-20 patients on LA CAB+RPV and 5-10 controls will be included from each participating centre to represent a proportionate spread from the study sites, but this will be dependent on local LA CAB+RPV uptake. Oversampling may be performed in the larger centres in order to maintain an overall sample size of up to $^{\sim}150$ on LA ART.

In addition, approximately three healthcare workers in different roles at each participating clinic will be interviewed and asked to complete a questionnaire.

11.2.1. Inclusion criteria for observational study using routinely collected clinic data

- 1. Understands the participant information and study requirements and has capacity to consent.
- 2. Willing to comply with study procedures
- 3. Age 16 years or above
- 4. Is a member of one of the following groups:
 - LA group PLWH who have been recently switched (within the prior 6 months) or are prospectively switched to LA CAB+RPV during the enrolment period. This includes those who have received LA CAB+RPV outside of BHIVA criteria or on compassionate grounds.
 - Oral ART group PLWH who are demographically similar but not eligible for LA CAB+RPV according to BHIVA eligibility criteria and who continue oral ART within the study period (e.g. those who are HBVcoreAb+ or who have an underlying drug resistance mutation that precludes use of LA CAB+RPV). Intervention group to oral group will be matched 3:1 by calendar period and other key variables where possible.

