9.2. Secondary Objectives

2. ACCEPTABILITY:

- a. To explore the acceptability of LA CAB+RPV amongst PLWH and health care workers delivering the regimen through a participant questionnaire, healthcare practitioner questionnaire and qualitative research.
- b. To compare patient-reported outcomes including quality of life, treatment satisfaction and treatment preference in those on LA CAB+RPV compared to those who remain on oral ART (demographically similar but not eligible for LA ART)

3. FEASIBILITY:

- c. To describe the feasibility of using the regimen from a clinical and patient perspective through outcomes in the participant and healthcare practitioner questionnaires
- d. To explore barriers and facilitators to effective implementation of the LA CAB+RPV regimen
- **4. FIDELITY:** To describe the fidelity of regimen delivery and associated monitoring compared to intended use in BHIVA guidelines

5. EFFECTIVENESS:

e. To characterise the UK-wide population who are switched to LA CAB+RPV and indications for switch

- f. To describe virological and clinical outcomes at one year of therapy in those on LA CAB+RPV and in those remaining on oral ART (demographically similar but not eligible for LA ART)
- g. To identify where actionable adjustments to implementation can be made to optimise overall adoption, sustainability and effectiveness of LA CAB+RPV

10. Outcome Measures

There are no interventional components to the study. Service-specific approaches to implementation of LA CAB+RPV in use at the study sites at study outset will be described, contrasted and compared.

Objective	Outcome measures	
Implementation outcomes		
ADOPTION 1. To quantify the adoption cascade	 a. Proportion of clinical cohort eligible for LA CAB+RPV according to BHIVA guidance b. Proportion of eligible adults offered/discussed a switch to LA CAB+RPV c. Proportion who accept the switch to LA CAB+RPV d. Proportion who remain on LA CAB+RPV at one year and reasons for switching off the regimen 	

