ACCEPTIBILITY 2a. To explore the acceptability of LA CAB+RPV amongst PLWH and health care workers delivering the regimen through a participant questionnaire, healthcare practitioner questionnaire and qualitative research. 2b. To compare patient-reported outcomes including quality of life, treatment satisfaction and treatment preference in those on LA CAB+RPV compared to those who remain on oral ART (demographically similar but not eligible for LA ART)	 a. The acceptability and experiences of the regimen amongst participants (PLWH) and healthcare workers delivering LA CAB+RPV through outcomes in the participant and HCP questionnaires b. The patient reported outcomes will be described through: i. Outcomes in the participant questionnaire and treatment preference in those switched to LA CAB+RPV ii. HIV-related quality of life - HIVPROM (11) 	
FEASIBILITY	a. Outcomes in the healthcare worker and participant questionnaires	

	CORAL
3a. To describe feasibility through outcomes in the participant and healthcare practitioner questionnaires 3b. To explore barriers and facilitators to effective implementation	b. Experiences, barriers and facilitators at both the individual and service level from qualitative work
FIDELITY	 a. Proportion of injections delivered within the visit window b. Number of oral bridging courses per patient per year c. Fidelity to 2-monthly HIV viral load monitoring (+/- 2 weeks of target date)
Effectiveness outcomes	
EFFECTIVENESS 5a. To characterise the UK-wide population who are switched to LA CAB+RPV and indications for switch 5b. To describe virological and clinical outcomes at one year of therapy in those on LA CAB+RPV and in those remaining on oral ART (demographically similar but not eligible for LA ART)	 a. Proportion of those who begin LA CAB+RPV who remain virologically suppressed at 12 months (by FDA snapshot algorithm and intention to treat approach), and the proportion of those on oral ART who remain virologically suppressed at 12 months after the baseline date b. Proportion of each group who have experienced virological failure at 12 months c. HIV-related medical events at 12 months d. Change in CD4 count from baseline to month 12 (where available) e. Change in renal function (estimated glomerular filtration rate, eGFR) from baseline to month 12

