13.2. Benefits

There are no direct benefits to the participants. However, the benefit of conducting observational research includes advancing scientific understanding of how LA ART is being implemented in the UK; this knowledge may guide treatment recommendations to the benefit of people living with HIV.

14. Withdrawal from study

Withdrawal from the study may be required if the participant withdraws consent as they no longer wish to participate. The decision to withdraw and the reason will be documented in the eCRF. The participant will be informed that data and samples collected up to that point will be retained for the purposes of the study, with their permission.

If a participant is lost to follow-up they can remain in the cohort and their missed visits will be documented in the eCRF. It is important to allow data collection on these individuals in case they return at a later date as describing their outcomes is of interest.

If an individual transfers out to another clinic it may not be possible to collect their routine clinic data (e.g. viral load data) however they can still complete questionnaires and therefore can remain in the cohort. The reason the laboratory data is missing will be recorded in the eCRF.

15. Fthical Considerations

The investigator(s) will ensure that this study is conducted in full conformity with the 7^{th} revision of the 1964 Declaration of Helsinki. The study will be conducted in accordance with the guidelines laid down by the International Conference on Harmonisation for Good Clinical Practice (ICH GCP E6 guidelines and Addendum ICH GCP E6 (R2)).

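### The oral ART group is defined partly by continuing oral ART after baseline, which cannot be verified at consent and permits selection on persistence, while the LA group is defined by starting

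*Protocol*

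**What the plan says.** Section 11.2.1, criterion 4, sets out the two groups. The oral group is people not eligible for LA CAB+RPV under BHIVA criteria "who continue oral ART within the study period". The LA group is people switched within the prior 6 months or who "are prospectively switched to LA CAB+RPV during the enrolment period". The LA definition does not require them to stay on the regimen.

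Objective 5b (item f in section 9.2) describes outcomes at one year "in those remaining on oral ART (demographically similar but not eligible for LA ART"). Sections 6 and 17 use similar wording for the comparator of about 50 adults.

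The effectiveness rows of section 10 give the LA outcome as "Proportion of those who begin LA CAB+RPV who remain virologically suppressed at 12 months (by FDA snapshot algorithm and intention to treat approach"). The oral outcome is "the proportion of those on oral ART who remain virologically suppressed at 12 months after the baseline date", with no snapshot or intention-to-treat label.

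On leaving the study, section 14 says: "Withdrawal from the study may be required if the participant withdraws consent as they no longer wish to participate". On missing people it says: "If a participant is lost to follow-up they can remain in the cohort and their missed visits will be documented in the eCRF". People who transfer to another clinic can also remain.

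Section 17 explains that the oral group is there to indicate what would have happened without the switch, and that the groups will not be formally compared at this stage.

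**The concern.** An inclusion criterion should be decidable on the day a person enters. This one refers to what the person does afterwards. If a site or analyst applies it as written, an oral participant who stops ART, or who moves to LA CAB+RPV, no longer fits the group definition. An LA participant who stops LA still fits theirs.

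People who stop treatment are the ones most likely to lose suppression. Leaving them out of one group and keeping them in the other would flatter the oral figures for suppression, virological failure and HIV-related events. It would also undercut the group's stated purpose, because stopping treatment is part of what happens to people who do not switch. Objective 2b sets patient-reported outcomes for the two groups side by side, so membership matters beyond virology.

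**Working it through.** **The plan's own figure.** Section 17 plans at least 150 LA and about 50 oral participants, and section 11.2.1 matches 3:1. 150 / 3 = 50, so the sizes agree. There is no alpha, power or effect size to reproduce.

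**The sections side by side.**

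| Feature | LA group | Oral group |
|---|---|---|
| Membership (11.2.1) | Met by the switch | Not eligible for LA, and continuing oral ART in the study period |
| Decidable at entry? | Yes | Not the second part |
| 12-month suppression (10) | All who begin; snapshot and intention to treat | Counted from the baseline date; no such label |
| Lost to follow-up or transferred (14) | Can remain in the cohort | Can remain in the cohort |
| Stops ART, or oral participant moves to LA | Stopping LA: still among those who began | Not addressed; conflicts with the literal criterion |

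The LA definition also accepts people treated outside BHIVA criteria. An oral participant who moved to LA during enrolment would therefore fit the LA definition and conflict with the oral one. The protocol does not say in which group that person is counted.

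**Possible size.** The protocol gives no stopping rate for oral ART, so every rate here is an assumption. Let *s* be the share who stop ART or move to LA, *p* the suppression among continuers, and *q* the share of leavers scored as suppressed.

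- Continuers only: *p*
- All enrolled: *p*(1 − *s*) + *qs*
- Overstatement: *p* − [*p*(1 − *s*) + *qs*] = *s*(*p* − *q*)

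Take *p* = 95% and *q* = 0 (every leaver a failure), with n = 50:

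| *s* | Leavers | All enrolled | Overstatement |
|---|---|---|---|
| 2% | 1 | 0.95 × 0.98 = 93.1% | 1.9 points |
| 5% | 2.5 | 0.95 × 0.95 = 90.25% | 4.75 points |
| 10% | 5 | 0.95 × 0.90 = 85.5% | 9.5 points |
| 15% | 7.5 | 0.95 × 0.85 = 80.75% | 14.25 points |

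For scale, the 95% half-width for a proportion of 95% at n = 50 is 1.96 × √(0.95 × 0.05 / 50) = 0.060, about 6 points. The overstatement passes that when *s* exceeds 0.060 / 0.95, or about 6.4%.

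Setting *q* = 0 gives the largest value for each *s*. The overstatement shrinks as more leavers are scored as suppressed, and is nil if *q* = *p*.

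**The case against.** The strongest reply is that the phrase is only a label for people who stay on oral ART and do not move to LA. The text says within the study period, not throughout it. The examples given (hepatitis B core antibody, a resistance mutation) explain why these people are not moving. An inclusion criterion governs entry, section 11.2.2 has no exclusion for later ART changes, and section 14 names only withdrawal of consent as a ground for leaving. Section 10 anchors the oral outcome at the baseline date. How leavers are analysed is ordinary SAP content. The study is descriptive, its primary outcome is the adoption cascade, and no formal comparison is intended.

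Much of this stands. A reader might infer that the oral results will describe persisters only. The documents do not support that: nothing orders removal, and section 14 points towards retention. Nor does *any* change of treatment conflict with the criterion, because moving from one oral regimen to another is still continuing oral ART. Only stopping ART or moving to LA does.

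Two parts do not stand. Section 14 covers withdrawn consent, loss to follow-up and transfer, but neither stopping ART nor moving to LA. Being kept in the cohort also does not settle whether someone still counts in a group defined by continuing. And although a SAP can set the analysis population, eligibility is a protocol rule: sites enrol against section 11.2.1 and record deviations under section 15.1.3. If baseline status is what was meant, the text should say so.

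**Conclusion.** The point holds as an ambiguity that permits bias, not as a bias that the protocol fixes. The oral criterion looks past baseline and is not symmetrical with the LA criterion. The missing snapshot and intention-to-treat label on the oral outcome leaves that asymmetry unresolved.

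The direction, if the criterion is applied literally, is upward for oral suppression. The size is unknown. The range of about 2 to 14 points rests on three assumptions: 2-15% stop, 95% of continuers are suppressed, and all who stop count as failures. If stopping is rare, the effect lies within sampling error for 50 people. With no formal comparison planned, the consequence is a descriptive benchmark that may look too good beside the LA figure. That is of moderate importance, and the wording should be corrected.

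**What to change.** 1. In section 11.2.1, define the oral group by status at the baseline date: on oral ART, not eligible for LA CAB+RPV under BHIVA criteria, and with no switch to LA planned at that date.
2. State that all enrolled oral participants stay in the oral group for the 12-month outcomes whatever later happens to their ART, with the date and reason of any stop or move recorded.
3. In section 10, score oral suppression by the same approach as the LA group ("by FDA snapshot algorithm and intention to treat approach"). Without this step, keeping people in the group does not settle how they are counted.
4. In objective 5b, wherever it appears, refer to those on oral ART at baseline in place of those remaining on it. Align the matching phrases in sections 6 and 17.

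The cost is protocol wording, plus a date and a reason for the few who stop or move. No extra participants or procedures are needed. The downside is that the oral figures may look slightly less favourable.

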11.2.2. Exclusion from observational study using routinely collected clinic data

- 1. In the opinion of the investigator is unable or unwilling to comply with the study requirements
- 2. Aged < 16 years of age

12. Study procedures

12.1. Identification of potential participants for observational study using routinely collected clinic data

Potential participants will be identified by a member of the site HIV clinical research team and invited to participate by their HIV doctor/nurse or a member of the research team, who will briefly explain the study outline either in-person, by telephone or email. If the potential participant expresses an interest in joining the study then they will be sent the electronic participant information sheet (PIS) and informed consent form (ICF), or the informed consent process can be completed in person by the research team if this better suits the potential participant's needs.

12.2. Informed consent

Individual-level consent to join the observational cohort will be sought from study participants (adults on LA CAB+RPV and comparator group on oral ART) prior to any study procedures. Potential observational cohort participants will be identified by the local research team. Potential participants will be briefly verbally introduced to the aims and requirements of the study by the local research team. Those who are deemed to have mental capacity to provide informed consent and are keen to proceed to receiving the full participant information (PIS) will then we provided with a link to the on-line participant information sheet (PIS) and informed consent form (ICF) via email or text message by the local research team. If the participant cannot complete on-line informed consent for any reason, written consent will be sought by the site research team using a paper-based PIS and ICF. Once a participant has provided informed consent and joined the study the ICF will be filed locally and the coordinating centre team will be notified.

The participant will be informed that participation is voluntary and that he/she can withdraw his/her consent at any time without any consequence for his/her treatment or future relationship to the clinic/hospital. The PIS must be read and the ICF signed before any study related activities can begin.

For the qualitative work (in-depth interviews with a sub-set of cohort participants and interviews/focus group discussions and questionnaire with healthcare workers) a separate informed consent process will be undertaken by a member of the research team at Brighton and Sussex Medical School. The qualitative participant information and informed consent process will be also be administered on-line where possible but paper-based PIS/ICFs will be available where necessary.

12.3. Prospective observational study

12.3.1. Collation of routinely collected clinic data

Routine blood testing is performed as part of routine clinical care per the BHIVA HIV Monitoring Guidelines [9]. No research blood testing is performed. Routinely collected clinic data from the participants in the LA CAB+RPV group and oral ART comparator group will be submitted by the participating clinic investigator (research nurse or research assistant) at

baseline, 6 and 12 months via a REDCap case report form. HIV viral load will be collected at every time point that it is measured from the time of participant enrolment.

It is possible to include data on consenting adults who started the injectable regimen up to 6 months prior to the clinic being activated as a study site. These individuals will not be asked to complete the participant questionnaires but their routinely collected clinic data is still valuable to the study objectives.

Continuation of the cohort study period for a longer duration may be possible if funding is made available for cohort and data management. Participants would be contacted to ask whether there are willing for their routinely collected clinic data to be shared beyond the initial 12-month data collection period. This would not involve any additional procedures for the participant.

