11.1.1. Observational study using routinely collected clinic data

The study will capture data from HIV-1 positive adults receiving long-acting cabotegravir and rilpivirine as part of their treatment regimen. All HIV-1 positive adults (≥ 16 years) who initiated long-acting cabotegravir and rilpivirine-based ART any time from 6 months prior to study site initiation will be eligible to be included in this study. A demographically similar comparator group on oral ART will also be invited to join the study. Routinely collected medical data from eligible and consenting participants' medical records will be extracted at key intervals, as laid out in the Schedule of Activities (see section 12.3.4), and entered into an electronic data capture system (Research Electronic Data Capture, REDCap). Variables of interest include demographic data, HIV treatment history, laboratory findings, which are all collected routinely in line with the BHIVA monitoring guidelines.

The total duration of patient follow-up is at least 1 year from the time of enrolment. The final analysis will be conducted following database lock after the last study participant has reached the 12 months treatment milestone and all data queries have been resolved.

Patients who received LA ART outside of the BHIVA criteria e.g. on compassionate grounds are of interest and can be included in the prospective study; the reasons for BHIVA criteria ineligibility and outcomes (duration of therapy, virological and clinical) will be described.

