12.3.2. Data items to be collected

The following items are collected:

- **Demography and basic information:** Date of birth, gender, country of origin, ethnicity, height, weight, date of first HIV-1 positive test and mode of HIV-1 transmission.
- Laboratory data: HIV VL at all points of testing, CD4 count where available, hepatitis C status, hepatitis B serology, as well as routine laboratory data that describe the function of the kidneys and liver. Biomarkers of metabolic disease will also be collected.
- Medical treatment: Current HIV treatment regimen, prior ART regimen, number of HIV drugs and drug classes used in the past, year of first treatment regimen. Medical treatment related to co-infections and co-morbidities.
- Clinical events: Medical history and any interim clinical events (including AIDS, myocardial infarction, stroke, kidney failure, liver failure, cancer, bone fractures etc).
 Interim medical events will be assessed for seriousness and relatedness (an adverse reaction that may be possibly, probably or definitely related to the injections).

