12.3.4. Schedule of Activities

The following activities will take place for PLWH enrolled in the prospective cohort study.

Table 1. Schedule of Activities for Participants

·	individual baseline M0*	Individual month 6 (+/- 2 months)	Individual month 12 (+/- 2 months)
Informed consent process	Х		
ROUTINELY COLLECTED CLINIC DATA			
Baseline characteristics, height	X		
Comorbidities	Х	Х	Χ
HIV / ART history	Х		
HIV VL (all interim VLs collected)	Х	X	Χ
CD4+ T cell count (if available)	Х	X	Χ
Creatinine, eGFR, HbA1c, lipids, ALT, weight (if available)	X	X	X
Interim medical events requiring medical attention/treatment		X	X
QUESTIONNAIRES			
Participant questionnaire: • Section A: LA CAB+RPV treatment experience and preference • Section B: HIV PROM (oral comparator group only complete section B)	Х	X	Х
QUALITATIVE			
In-depth interviews (~n=3 at each site)		X	

^{*}Individuals who have been switched to LA CAB+RPV during the 6 months prior to the clinic site being opened for enrolment are eligible to join the prospective cohort study for the collection of routine clinic data. Their individual baseline is the date that they were switched to LA CAB+RPV.

eGFR = estimated glomerular filtration rate, ALT = alanine transaminase, HbA1c = haemoglobin A1c, HIV VL = HIV viral load, HIV PROM = HIV patient reported outcome measures

Approximately three healthcare workers from each participating clinic will be asked to complete a single questionnaire and engage with an interview / focus group discussion.

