16.4. Data sharing

We will be proactive in ensuring that this valuable data is used to its full potential. The Study Management Group (SMG) will welcome proposals for collaborations from other academic groups as well as the study funders. Those potentially interested should submit a proposal to the SMG containing information about the project, analysis plan and data requirements. Proposals will then be discussed by the SMG and will be approved if it is felt to be scientifically valid with appropriate methodology. Any request for sharing the study dataset must be approved by the SMG.

17. Statistical Considerations

As this is primarily a descriptive study no formal power calculation is required. The inclusion of a group of people receiving oral ART is to give an indication of the outcomes that would be seen had the participant not switched to LA CAB+RPV, but it is not our intention at this stage to formally compare groups due to the expected differences in characteristics of the two groups. Across all study sites the aim is to recruit a minimum of 150 adults receiving LA CAB+RPV into the prospective cohort study and ~50 adults who remain on oral ART as the comparator population. Around 20-30 participants will participate in the qualitative study.

Detailed description of the statistical analyses, any deviation from the protocol, and assumptions employed will be presented in a detailed Statistical Analysis Plan (SAP) that will be prepared prior to database closure and initiation of any statistical analyses below.

The demographic, clinical and treatment characteristics of all participants (age, BMI, race/ethnicity, co-morbidities, ART history) will be presented as summary statistics (mean,

median, standard deviation, IQR, maximum and minimum for continuous measurements, and numbers and proportions for categorical measurements), stratified by group (LA CAB+RPV, oral ART).

We anticipate most participants will have virological suppression at baseline; in such participants the proportion of participants with sustained virologic suppression at 6 and 12 months will be described. For those who are not virologically suppressed at enrolment, changes in viral load will be described.

Amongst those with available longitudinal CD4 count data, renal data (creatinine / eGFR) and lipid data (total cholesterol, total:HDL cholesterol ratio and triglycerides) the mean change from baseline in the LA CAB+RPV group and the oral group will be described.

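### LA participants enrolled after their switch are timed from the switch, but Section 12.3.1 starts viral load collection at enrolment, contradicting 12.3.2 and Table 1, and Section 17 mixes the two dates

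*Protocol*

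**What the plan says.** **Who can enrol late.** Protocol Section 11.2.1 admits to the LA group "PLWH who have been recently switched (within the prior 6 months"), as well as people switched prospectively. Section 12.3.1 allows consenting adults who started up to 6 months before the site was activated.

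**Time origin.** The footnote to Table 1 (Section 12.3.4) says of these people: "Their individual baseline is the date that they were switched to LA CAB+RPV". Months 6 and 12 therefore run from the switch.

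**Viral load collection.**
- Section 12.3.1: "HIV viral load will be collected at every time point that it is measured from the time of participant enrolment".
- Section 12.3.2: "HIV VL at all points of testing", with no start date.
- Table 1: "HIV VL (all interim VLs collected"), marked at month 0, month 6 and month 12.

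**Suppression groups.** Section 17 describes sustained suppression at 6 and 12 months among those suppressed at baseline. The next sentence reads: "For those who are not virologically suppressed at enrolment, changes in viral load will be described".

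**Follow-up.** Section 11.1.1: "The total duration of patient follow-up is at least 1 year from the time of enrolment". The sentence after it ties the final analysis to the 12-month treatment milestone.

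**Outcomes.** Section 10 lists "Proportion of those who begin LA CAB+RPV who remain virologically suppressed at 12 months", by FDA snapshot and intention to treat. It also lists the proportion who have had virological failure by 12 months, and fidelity to 2-monthly viral load monitoring.

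**The concern.** For someone who consents some months after switching, switch and enrolment are different dates, one at the start of LA treatment and one during it. The protocol uses both without saying which governs.

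Three things are at stake. First, virological failure by 12 months counts whether a failure ever occurred, so it needs every viral load from the switch onward. A site that extracts data by 12.3.1 would leave out results that a site working from Table 1 would supply. Second, a person suppressed at the switch who rebounds before consent meets both descriptions in Section 17: suppressed at baseline and not suppressed at enrolment. Third, and apart from the viral load sentence, consent is given after the switch. It is sought from people described as being on the LA regimen (Section 12.2) or receiving it (Section 11.1.1). People who stopped, failed or left care early may be harder to enrol, although the effectiveness denominator is everyone who begins LA.

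Any resulting error in 12-month failure or stopping would run towards the hypothesis in Section 8, which expects high effectiveness.

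**Working it through.** The protocol gives no power calculation or expected event rate, so there is no figure to reproduce. The check has two parts.

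**1. The passages side by side, for a person who switches at day 0 and consents at month 6**

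| Item | Clock used | Consequence |
|---|---|---|
| Table 1 footnote | Switch | Month 12 is 6 months after consent |
| 12.3.1 | Enrolment | Viral loads in months 0-6 not collected |
| 12.3.2 and Table 1 | All tests; month 0 and interim | Same viral loads are collected |
| Section 17, suppressed group | Baseline (switch) | Pre-enrolment rebound does not remove the person |
| Section 17, non-suppressed group | Enrolment | The same person also fits here |
| 11.1.1 follow-up | Enrolment | At least 18 months after the switch (6 + 12) |

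At 2-monthly testing there are 12/2 = 6 viral loads a year, and up to 6/2 = 3 of them fall before enrolment.

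**2. Possible size of under-enrolment**

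The documents give none of the inputs, so these are assumptions: true 12-month freedom from stopping or failure S; enrolment uniform over 0-6 months after the switch; only event-free people enrol.

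Constant hazard: h = -ln(S)/12. Late enrollees show S multiplied by the mean of exp(ht) over 0-6 months, which is S × (S^(-1/2) - 1)/(6h).

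For S = 0.90: 6h = 0.0527, S^(-1/2) = 1.0541, ratio = 0.0541/0.0527 = 1.0268, so 0.90 × 1.0268 = 0.924.

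Front-loaded: if a share p of the events falls evenly over months 0-6, put a = p(1 - S). Late enrollees show S × (-ln(1 - a))/a. For S = 0.90 and p = 60%, a = 0.06 and 0.90 × 0.0619/0.06 = 0.928.

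| True S | Event pattern | Late enrollees show | Pooled, if half enrol late |
|---|---|---|---|
| 95% | Constant | 96.2% | 95.6% (+0.6) |
| 90% | Constant | 92.4% | 91.2% (+1.2) |
| 90% | 60% in months 0-6 | 92.8% | 91.4% (+1.4) |
| 90% | 75% in months 0-6 | 93.6% | 91.8% (+1.8) |
| 85% | Constant | 88.5% | 86.8% (+1.8) |
| 85% | 75% in months 0-6 | 90.2% | 87.6% (+2.6) |

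The pooled figure is 0.5 × S + 0.5 × the late-enrollee figure. At 90% and constant hazard, 1.2 points is 0.012 × 150 = about 2 of the 150 planned LA participants. If a quarter enrol late it is 0.25 × 2.4 = 0.6 points.

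**Wider range.** With a fixed lag L and true risk q, the share with an event before enrolment is e = 1 - (1 - q)^(L/12). If those people never enrol, late enrollees show (q - e)/(1 - e). If they enrol but the early event goes unrecorded, late enrollees show q - e. With half enrolling late at L = 6 and nobody with an early event enrolling, true risks of 5%, 10% and 15% appear as 3.8%, 7.6% and 11.4%. Over q = 5-15%, L = 3-6 months, 25-100% enrolled late and 0-100% of early events lost, the understatement runs from 0 to 7.8 points. The top needs every LA participant to enrol at month 6 and every earlier event to go unrecorded.

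**The case against.** The strongest reply is that this is loose wording with little effect. Much of it stands, and it rules out several stronger readings that a reader might infer.

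- **That early viral loads are discarded by rule.** Section 12.3.2 and Table 1 both call for them, so the text contradicts itself and does not settle on discarding them.
- **That a rebound before consent removes someone from the sustained-suppression denominator.** That denominator is set at baseline, which is the switch for late enrollees. The fault is overlap between the two groups.
- **That early stoppers are excluded.** Eligibility rests on having started LA. Nothing requires current treatment, and Section 17 describes discontinuations with reasons. Under-enrolment is a risk arising from consent and from how the group is described.
- **That every 12-month outcome looks too good.** The snapshot depends on status at month 12, so missing early viral loads alone do not bias it; under-enrolment could. For monitoring fidelity the direction is uncertain: tests not collected would look like missed tests if counted from the switch, which lowers fidelity.
- **That the primary outcome is affected.** Outcome 1d comes from the clinic registry, which includes people who have already started (Sections 11.1.5 and 12.6).
- **That follow-up in 11.1.1 prevents the month-12 outcome.** It is a minimum and runs past month 12 from the switch.

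The pooled error of about 1 point is also small beside the 95% half-width at 90% with 150 people: 1.96 × √(0.9 × 0.1/150) = 4.8 points. A systematic error does not shrink with sample size, however, and the contradiction in extraction instructions remains whatever its size. Whether to use delayed entry, or to make people enrolled by first injection the main result, is a trade-off that belongs in the SAP.

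**Conclusion.** The point holds as an internal contradiction with a possible, unquantified effect. The protocol needs one time origin and one start of viral load collection for LA participants enrolled after their switch. Followed literally, 12.3.1 may miss virological failures between switch and enrolment and leaves monitoring fidelity unassessable for those months. Section 17 lets one person fall into both suppression groups.

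Under-enrolment of early stoppers is a separate risk. The 92.4% shown for a true 90% applies to late enrollees only. It rests on a constant hazard, uniform entry over 0-6 months and nobody with an early event enrolling. Pooled, it is about 1 point if half enrol late, and 0 if early stoppers enrol and their data are captured. The protocol does not give the share enrolled late. This should be fixed before data are extracted; it does not threaten the primary outcome.

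**What to change.** - **Section 12.3.1:** collect viral loads from the individual baseline, which is the date of switch for the LA group, in line with 12.3.2 and Table 1.
- **Section 17:** define both suppression groups at individual baseline, using the last viral load on or before the switch for the LA group.
- **Section 11.1.1:** state follow-up as 12 months from individual baseline.
- **Sections 11.2.1 and 12.1:** state that every starter in the look-back period is approached, including those who have already stopped LA.
- **Reporting:** show late enrollees separately as a sensitivity analysis for the 12-month outcomes.

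The cost is wording and a little more extraction from existing clinic records. It depends on consent covering routine data from before enrolment, which cannot be checked here because the consent pages are not in the reviewed text.
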